CDW data will be used to assess patient baseline characteristics (e.g., age, demographics, past medical history, prior healthcare utilization) as well as outcomes (i.e., ED utilization, readmission, mortality, and falls). In this way, the same data source is used to identify outcomes for both intervention and control patients.

Chart Review data

Chart review will be used to validate the TeleGRACE dose classification that is based on CDW data (see Per-Protocol analysis described below).

Follow-up Period

Patients will be followed for one year from the date of discharge from their index hospitalization. Unlike clinical trials that require in-person outcome assessments and hence implement “windows” for data collection, this evaluation will use electronic health record data for outcome assessment and hence no windows will be specified.

ANALYSIS PLAN

Intention-to-Treat Analysis

We will compare baseline characteristics between TeleGRACE patients and control patients using chi-square tests for categorical data and t-tests for continuous characteristics.

In the primary intention-to-treat (ITT) analysis, we will compare outcomes between patients randomized to usual care and those to TeleGRACE adjusting for the baseline characteristics that are significantly different by logistic regression for the binary outcome and Poisson regression for count data. If the sample size is sufficient, we will examine the effect of the TeleGRACE program by site of receipt of primary care services.

Per-Protocol Analyses

Not all patients who are randomized to receive TeleGRACE will receive services from the TeleGRACE staff. This situation is anticipated for patients who decline GRACE and others who become ineligible after discharge from the index hospitalization but before their first virtual home visit post-discharge (e.g., patients who die, get readmitted, or move to a skilled nursing facility after discharge). In the exceptionally rare case, patients may be discharged from TeleGRACE due to safety concerns for our staff (e.g., sexually or physically aggressive behavior, unwillingness to cage animals, unwillingness to store firearms). The per-protocol analyses will be similar to the planned intention-to-treat analysis but will compare the outcomes between patients who received GRACE service versus patients in usual care.

Given the expected heterogeneity in the number of TeleGRACE visits, patients will be classified into four categories as follows:

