 - d. If there are more than 10% patients censored for the outcomes, we will conduct Cox-regression analysis for the hazard of death and risk-exposure adjusted Poisson regression for the number of readmissions and number of falls.

POWER

For **Aim 1** (effectiveness of TeleGRACE versus usual care), we expect to observe 2% and 8% 90-day all-cause mortality for the TeleGRACE and usual care patients, respectively. This projected effect size is conservative based on our propensity-score weighting analysis comparing GRACE patients with usual care patients. With 180 TeleGRACE and 360 usual care patients, the study has 0.96 power at detect the efficacy of TeleGRACE program with a one-sided normal test at a significance level 0.05. Considering a 10% drop-out, the analysis has 0.94 power to establish the TeleGRACE efficacy with the same effect size.

DATA MONITORING

Enrollment

We will closely monitor the randomization of TeleGRACE with the expected rate of 5 per month. We will plot the number of actual randomized patients and its expected number against the study time and update the figure on a monthly basis. Prior to the DSMB meeting, we will estimate the current randomization rate and project the final number of randomized patients by end of the fourth year with the current rate along with its 95% confidence interval based on the Poisson distribution. If the upper bound of the 95% interval is below the target number of 180. We will modify the enrollment strategy to ensure that we achieve the enrollment goal.

Interim Analysis

Since the observed effect size of in-person GRACE versus usual care is quite substantial with respect to 90-day all-cause mortality, we plan an interim analysis when a half of the enrolled patients can be evaluated for the primary outcome. One-sided normal testing will be applied for the interim analysis using O'Brien-Fleming group sequential test with the overall type error controlled at 0.05. The hypotheses are:

$$H_0: p_1 = p_2 \text{ vs. } H_1: p_1 < p_2,$$

where p_1 and p_2 stand for the 90-day all-cause mortality in TeleGRACE and usual care arms, respectively.

If the Z – test statistic crosses the boundary of -2.54 at the interim analysis, the trial will be recommended for stopping for efficacy; otherwise, the trial will continue to the end with the crossing boundary for the test statistic at -1.66. The overall power with the interim analysis for this study is 0.82.

Safety

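### The ITT rule lets prior utilization into the secondary count models only when it is imbalanced by chance, so precision that the planned data could supply is mostly left unused

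*Combined protocol and SAP*

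**What the plan says.** Under Data Sources, the CDW subsection states: "CDW data will be used to assess patient baseline characteristics (e.g., age, demographics, past medical history, prior healthcare utilization". The same sentence names that source for the outcomes: "as well as outcomes (i.e., ED utilization, readmission, mortality, and falls".

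The Intention-to-Treat Analysis section compares the arms at baseline "using chi-square tests for categorical data and t-tests for continuous characteristics". It gives no significance level for these tests. The outcome models follow, "adjusting for the baseline characteristics that are significantly different by logistic regression for the binary outcome and Poisson regression for count data". No covariate is fixed in advance for any outcome.

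Item 3d of the Sensitivity Analyses (Discontinuous Eligibility Periods) adds, if more than 10% of patients are censored, "risk-exposure adjusted Poisson regression for the number of readmissions and number of falls". It names no prior count as a covariate.

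The Power section covers 90-day mortality only. No power or precision is given for readmissions, ED use or falls.

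**The concern.** In a randomized trial, a baseline covariate improves precision to the extent that it predicts the outcome. Whether it happens to differ between arms is a separate question. Past use is the natural baseline value of later use, yet the rule selects covariates on imbalance and ignores prognosis.

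What is at stake is how well the secondary count outcomes can be estimated. As a yardstick, the earlier VA-GRACE results in the Overall TeleGRACE Project Rationale can be read as rate ratios:

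- 7.1% fewer ED visits: ln(1 − 0.071) = −0.074
- 14.8% fewer 30-day readmissions: ln(1 − 0.148) = −0.160
- 37.9% fewer hospital admissions: ln(1 − 0.379) = −0.476

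Against a standard deviation of about 0.13 for the log rate ratio (derived below under assumed inputs), the first two would be hard to resolve and the third would not.

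**Working it through.** **1. The plan's own figure.** The only stated power is for the primary outcome: "we expect to observe 2% and 8% 90-day all-cause mortality for the TeleGRACE and usual care patients, respectively", with 180 and 360 patients and a one-sided 0.05 test. With unpooled variance:

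Φ(0.06 / √(0.02×0.98/180 + 0.08×0.92/360) − 1.645) = Φ(0.06/0.01770 − 1.645) = Φ(1.745) = 0.9595, against 0.96 stated.

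With 10% drop-out (162 and 324): Φ(0.06/0.01866 − 1.645) = Φ(1.571) = 0.9419, against 0.94 stated.

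Both reproduce. Neither bears on the count outcomes, and nothing below changes them.

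**2. How often the rule admits prior use.** Randomization makes the null hypothesis of the baseline test true, so a 0.05 screen (assumed) passes prior use in about 5% of trials.

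**3. Standard errors without adjustment.** The documents give no event rates, dispersion or correlation. Assume a mean of 1 event a year in each arm, frailty variance 1 and full follow-up.

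- Poisson model standard error of the log rate ratio: √(1/180 + 1/360) = 0.091. This depends on the expected number of events only.
- True standard deviation: the marginal variance of a count is 1 + 1×1² = 2, so √(2/180 + 2/360) = 0.129.

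If the counts are this overdispersed, the plain Poisson standard error is too small by a factor of √2.

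**4. Simulation.** There were 2,000 trials per row at 180 TeleGRACE and 360 usual care, with Poisson counts and correlated log-normal frailties. Three analyses were compared: no adjustment, always adjusting for log(1 + prior count), and the plan's rule (adjust only if the baseline t-test has p < 0.05).

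| Observed correlation, prior to follow-up | Prior count selected | SD: none / always / plan's rule | Variance cut: always | Variance cut: plan's rule | Poisson model SE: none / always |
|---|---|---|---|---|---|
| 0.11 | 4.9% | 0.1300 / 0.1293 / 0.1296 | 1.1% | 0.6% | 0.0916 / 0.0917 |
| 0.25 | 5.4% | 0.1292 / 0.1249 / 0.1276 | 6.6% | 2.6% | 0.0917 / 0.0919 |
| 0.43 | 5.0% | 0.1308 / 0.1190 / 0.1276 | 17.3% | 4.9% | 0.0916 / 0.0918 |

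A separate run under the same assumptions gave cuts of about 1%, 6% and 18% at correlations 0.11, 0.26 and 0.43.

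**5. What the reported interval would show.** The last column does not fall when the covariate is added: the Poisson standard error stays at 0.092. A robust standard error does fall, from 0.128 to 0.116 at correlation 0.43.

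**6. Allocation.** The Randomization section gives 1 control to 2 intervention, which conflicts with 180 TeleGRACE and 360 usual care. That is a separate matter. With the arms reversed, the cuts from always adjusting are 1.2%, 7.5% and 16.5%, so this point does not depend on how the conflict is resolved.

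**The case against.** Several arguments on the other side have force.

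- **Prior use is not shut out.** A reader might infer that the count models leave it out altogether. They do not: it enters when the baseline test is significant, and the plan's rule recovers part of the gain (about 1%, 3% and 5%, against 1%, 7% and 17%). What stands is that its entry is left to chance.
- **Intervals would not narrow under the model as planned.** A reader might expect one extra term to shorten the confidence intervals. With "Poisson regression for count data" and its model-based standard error, it would not (step 5). The estimate becomes steadier, but the reported interval shows this only with a variance that allows for overdispersion. This objection stands in full, and it shapes the fix.
- **The data may not all be there.** The CDW sentence names prior healthcare utilization. It gives no look-back window, does not name prior falls (though its list is only of examples), and does not say whether prior non-VA ED visits are captured, although the ED outcome covers both VA and non-VA visits. The plan also does not say that ED use is analysed as a count; only readmissions and falls are named as numbers of events.
- **The size is assumed throughout.** At a weak correlation the gain is about 1%. The simulation also ignores follow-up cut short by death.
- **The root is the general covariate rule.** True, and a prespecified covariate list would cover this point. Prior counts still deserve naming because they are the baseline values of these outcomes.

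**Conclusion.** The point holds as a modest matter of efficiency. The ITT section selects covariates by baseline significance, so a likely predictor that the trial already plans to extract enters the count models in about 1 trial in 20. Always adjusting would cut the true variance of the log rate ratio by about 1% to 18%. At the upper end this is worth 1/(1 − 0.18) = 1.22, or about 22% more patients; at the lower end, about 1%.

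These figures rest on an assumed mean of 1 event a year, frailty variance 1, correlations of 0.11 to 0.43, full follow-up and a 0.05 screen. The documents supply none of these.

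A reader might go further and infer bias in the treatment effect, or a weakness in the primary analysis. The documents do not support either. Randomization protects the unadjusted comparison, and the mortality power calculation involves no count covariate. The improvement is optional but cheap.

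**What to change.** In the Intention-to-Treat Analysis section, add wording to this effect:

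*Each count outcome (readmissions; ED visits if analysed as a count; falls where CDW can supply the prior count) will be adjusted for the log of one plus the patient's number of the same events in a defined window before the index admission, index stay excluded, regardless of baseline balance. Standard errors will be robust, or a quasi-Poisson or negative binomial model will be used.*

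The plan should state the length of the window and say which of the three variance options applies. The same covariate and variance should carry over to the exposure-adjusted Poisson model in item 3d of the Sensitivity Analyses.

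The cost is one model term per outcome, plus confirmation before the text is fixed that prior falls and prior non-VA ED visits can be obtained. No extra patients are needed. The variance choice matters as much as the covariate: without it, the Poisson intervals stay too narrow whenever counts are overdispersed, and the gain from adjustment does not appear in the report.

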	Q1 OCT - DEC	Q2 JAN - MAR	Q3 APR - JUN	Q4 JUL - SEP	Q1 OCT - DEC	Q2 JAN - MAR	Q3 APR - JUN	Q4 JUL - SEP	Q1 OCT - DEC	Q2 JAN - MAR	Q3 APR - JUN	Q4 JUL - SEP	Q1 OCT - DEC	Q2 JAN - MAR	Q3 APR - JUN	Q4 JUL - SEP	Q1 OCT - DEC	Q2 JAN - MAR	Q3 APR - JUN	Q4 JUL - SEP
Program Development																				
TeleGRACE Active Implementation																				
Outcome Assessment																				
Business Case Analysis																				
Implementation Analysis																				
Effectiveness Analysis																				
Manuscripts, final reporting																				

THIS ANALYSIS PLAN FOCUSES ONLY ON EFFECTIVENESS

To examine the effectiveness of the TeleGRACE program, we designed a randomized controlled implementation trial (RCT) powered for the primary outcome of 90-day all-cause mortality. We will also examine its effectiveness for the secondary outcomes including 90-day readmissions, 1-year ED utilization (VA and non-VA), 1-year all-cause readmissions, 1-year mortality, as well as patient, caregiver, and staff satisfaction. We hypothesize that patients who receive TeleGRACE will have lower 90-day mortality than patients in usual care.

METHODS

The TeleGRACE project will be a prospective, randomized controlled trial. The unit of randomization is the patient. **This project is an evaluation of a clinical program and is classified as quality improvement and not research.**

Intervention: In-Person versus Telehealth

The GRACE program involves geriatric-focused home visits by a nurse practitioner and a social worker followed by multidisciplinary meetings to discuss each Veteran's plan of care along with ongoing collaboration with VA primary care. This "in-person" model has been in effect at the Indianapolis VA medical center since 2010. In the telehealth approach, a staff member will be trained to conduct home visits using the GRACE protocol and will use video telehealth (i.e., VA video connect [VVC]) from the patient's home to connect with the GRACE multidisciplinary team members located at the coordinating center in Indianapolis. **The use of the virtual home visit instead of the in-person home visit is the only change that is made for the TeleGRACE program.** The multidisciplinary team meetings as well as the follow-up and coordination of care with the primary care PACT teams will be unchanged. The number of visits and the content of the assessments will be the same for TeleGRACE patients as for in-person GRACE patients.

Eligible Veteran Patients

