1. **Full TeleGRACE dose:** the patient received a virtual post-discharge transitional visit, followed by a virtual baseline visit with multidisciplinary team discussion, and then follow-up virtual discussion to ensure that the patient and caregiver agree with and understand the plan of care. These patients may receive additional follow-up contacts with the TeleGRACE/GRACE team members over the course of the one year follow-up period. Note: in the atypical situation where the patient did not receive a transitional visit but did receive a baseline assessment, the patient will still be classified as "full TeleGRACE dose").
2. **Transitional visit dose:** the patient received a virtual post-discharge transitional visit but did not receive a baseline visit. These patients may receive additional follow-up contacts (typically by telephone) with the TeleGRACE/GRACE team members over the course of the one-year follow-up period. In some cases, the patient may receive multiple transitional visits (e.g., after readmissions).
3. **Partial dose:** the patient received neither a post-discharge transitional visit nor a baseline visit but had other contact with the TeleGRACE/GRACE team (typically telephone visits).
4. **No TeleGRACE:** patients may have been contacted by the TeleGRACE/GRACE team in an attempt to schedule a visit, but these patients received no clinical visits or encounters. Patients who decline TeleGRACE services are included in this category. Please note: in a research randomized controlled trial, only patients who are potentially interested in participation are consented and then randomized. TeleGRACE is a quality improvement project, therefore enrollment follows procedures used in clinical care.

We will further examine the outcomes among patients across these 4 categories as well as the control patients.

Sensitivity Analyses

Considering the heterogeneity in the TeleGRACE patients, we plan to conduct the following sensitivity analyses

1. **Enrolled versus Randomized to TeleGRACE:** We will conduct the ITT analysis described above which compares patients *randomized* to TeleGRACE versus usual care controls. In addition, we will compare patients who *enrolled* in TeleGRACE versus control patients.
2. **Dose:** In addition to the description of TeleGRACE services as provided in the per-protocol analysis, the dose of the TeleGRACE program will be assessed in terms of:

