 - a. The total number of GRACE contacts (telephone, virtual or in-person) in the one-year post-discharge from the index event.
 - b. Typically, home visits are conducted by a dyad of a nurse practitioner and social worker. Given staffing constraints, some patients may only receive a visit by a social worker or a nurse practitioner but not both. Therefore, each transitional, baseline, and follow-up visit will be assessed to describe whether it was conducted by social work, nursing, or other staff.
 - c. A key element of the GRACE program is the development of a multidisciplinary plan via discussion at the weekly GRACE rounds. The number of times an individual patient is discussed by the entire team in the year post-discharge will

be recorded (the geriatrician's summary of the multidisciplinary discussion will be used to identify whether a patient was discussed during team rounds).

3. **Discontinuous Eligibility Periods:** Patients who become permanently ineligible for TeleGRACE (e.g., are readmitted and then subsequently discharged to a long-term care facility) will be censored on the date they became ineligible for the outcome measures because they became ineligible for services. However, this censoring plan will be implemented retrospectively because it is expected that the older persons who will be enrolled in this study may have intermittent periods of ineligibility (e.g., during a hospital stay and then followed by short-term rehabilitation stay). Such patients may still benefit from the intervention and hence will not be censored either from the intervention or control groups.
 - a. For all intervention patients, we will calculate the proportion of eligible days a patient is cared for by the GRACE team as: the number of days that the patient was under the care of the GRACE team divided by the total number of days the patient was potentially eligible for GRACE.
 - b. We will note whether the period of eligibility was either continuous or discontinuous.
 - c. For patients with a discontinuous eligibility period, we will describe the patterns of discontinuity. For example, some patients may have a short hospital stay early post-discharge but then receive a relatively long period of GRACE services in the year post-discharge. In contrast, other patients may have recurrent hospitalizations some of which may be followed by short-term rehab stays resulting in fragmented eligibility periods of relatively short durations.

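### A shared data source does not make fall detection equal: TeleGRACE adds recorded contacts in one arm, so the 1-year falls comparison may be biased, probably against the program

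*Combined protocol and SAP*

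**What the plan says.** Falls over one year are listed as a secondary outcome under METHODS, Outcome Measures, without codes, encounter settings, note types or severity. Under Data Sources, the CDW is named as the source of "outcomes (i.e., ED utilization, readmission, mortality, and falls", followed by the statement "In this way, the same data source is used to identify outcomes for both intervention and control patients". The Intention-to-Treat section assigns "Poisson regression for count data". Under Sensitivity Analyses, item 3d, the number of falls is one of the counts to be modelled if censoring exceeds 10%.

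The intervention itself consists of contacts: "The GRACE program involves geriatric-focused home visits by a nurse practitioner and a social worker followed by multidisciplinary meetings". For full-dose patients the plan adds: "These patients may receive additional follow-up contacts with the TeleGRACE/GRACE team members over the course of the one year follow-up period". Dose is to be measured partly as "The total number of GRACE contacts (telephone, virtual or in-person) in the one-year post-discharge from the index event". These contacts can be seen in the CDW, because "Chart review will be used to validate the TeleGRACE dose classification that is based on CDW data".

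Chart review is otherwise mentioned only for checking the exploratory nursing home data. The plan states no chart check of falls and no sensitivity analysis for unequal recording.

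**The concern.** A death or an admission creates its own record. A fall that leads to no acute care enters the record only if the patient has a contact at which it is mentioned and noted. The chance of recording therefore depends on how many contacts a patient has, and the intervention changes that number in one arm. The program writes entries into the same database from which the outcome is drawn.

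If falls noted at program contacts count, a true reduction in falls could be masked, or an apparent increase produced, by recording alone. The problem is sharper in the per-protocol and dose-category comparisons, where the groups are formed by the number and type of contacts received.

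**Working it through.** The plan gives no fall rate, recording rate or power for falls, so it has no figure of its own to reproduce. Its stated power of 0.96 concerns 90-day mortality only.

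**Step 1: does the text close the gap?** A common source gives equal detection only if an event has the same chance of entering it in both arms. Set side by side, the sections show that falls come from the CDW (Data Sources), that TeleGRACE contacts appear in the CDW (Chart Review data), that only the intervention arm receives them by design (Intervention; Per-Protocol Analyses), and that no definition of a fall excludes them (Outcome Measures). The gap stays open.

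**Step 2: what could it do?** This step is illustrative.

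From the POWER section: 180 TeleGRACE and 360 usual care patients. (The 1:2 control-to-intervention ratio under Randomization conflicts with these sizes and must be reconciled; the swapped sizes are checked below.)

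Assumed: b = 0.5 recorded falls per usual care patient-year, no overdispersion, a full year at risk for everyone, and a two-sided 0.05 Wald test on the log Poisson rate ratio. Let k be the relative chance that a fall is recorded in patients with TeleGRACE contacts, and c the share of the arm with contacts.

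- Observed RR = true RR × [1 + c(k − 1)]
- SE = √[1/(180 × b × observed RR) + 1/(360 × b)]
- Chance of a false finding of harm = Φ(ln(observed RR)/SE − 1.96)

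Example with true RR 1.0, k = 1.25, c = 1: observed RR = 1.25. Expected events are 180 × 0.5 × 1.25 = 112.5 and 360 × 0.5 = 180. SE = √(1/112.5 + 1/180) = 0.120. ln(1.25)/SE = 0.223/0.120 = 1.86, and Φ(1.86 − 1.96) = 0.46.

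| k | c | Observed RR (true 1.0) | Chance of false harm |
|---|---|---|---|
| 1.0 | any | 1.00 | 0.025 |
| 1.1 | 0.7 | 1.07 | 0.077 |
| 1.1 | 1.0 | 1.10 | 0.115 |
| 1.25 | 0.7 | 1.175 | 0.260 |
| 1.25 | 1.0 | 1.25 | 0.459 |
| 1.5 | 0.7 | 1.35 | 0.724 |
| 1.5 | 1.0 | 1.50 | 0.945 |

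With 360 TeleGRACE and 180 usual care patients, the k = 1.25 rows become 0.249 (c = 0.7) and 0.432 (c = 1), so the unresolved arm sizes hardly matter here.

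If the true RR is 0.80, then k = 1.25 with c = 1 gives 0.80 × 1.25 = 1.00, and the benefit disappears. With c = 0.7 it gives 0.80 × 1.175 = 0.94.

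**Step 3: which comparison is most exposed?** The intention-to-treat arm includes patients without contacts (c below 1), which dilutes the effect. A comparison restricted to patients who received services sets c = 1, so at k = 1.25 the distortion rises from 1.175 (at c = 0.7) to 1.25. Across dose categories, k itself may rise with the number of contacts.

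**The case against.** A reader might infer that falls will be detected more often under TeleGRACE, that the comparison is biased, and that usual care offers no matching chance for a fall to be recorded. The documents do not support that reading.

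- **No definition of a fall.** Nothing says that program contacts feed the falls variable or that those visits ask about falls. If only ED or inpatient coding is used, the added contacts matter much less.
- **Usual care patients have contacts too.** Eligibility requires a VA primary care visit within the prior two years, so a fall without acute care can be noted there. The difference is one of degree.
- **The direction could reverse.** The rationale cites 7.1% fewer ED visits and 37.9% fewer admissions with GRACE. If falls were recorded only at ED visits, and the chance of such a visit after a fall dropped in the same proportion, the observed RR would be 1 − 0.071 = 0.93 with no true effect. For the same reason, a definition limited to acute care would be a different outcome and not a neutral correction.
- **Dilution.** The plan expects this: "Not all patients who are randomized to receive TeleGRACE will receive services from the TeleGRACE staff".
- **The sentence on the shared source is true as written.** It does not claim equal detection.
- **Small consequence.** Falls are one secondary outcome, absent from the list in the Aim 1 statement and without a power calculation.

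All of this limits how firmly the point can be put. It does not remove it: the shared source is the only safeguard stated, and nothing excludes or checks falls recorded through the program.

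**Conclusion.** The point holds as an unaddressed risk of differential ascertainment, not as a demonstrated bias. It is conditional: if falls noted at TeleGRACE/GRACE contacts count, the 1-year falls comparison may be distorted, probably against the program, and the per-protocol and dose-category comparisons more so.

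The documents do not allow the amount to be estimated. The observed ratios of 1.07 to 1.50 rest on assumed values of k (1.1 to 1.5) and c (0.7 to 1); the probabilities also rest on an assumed fall rate and no overdispersion. They show only that modest differences in recording would be enough to mislead. Only this secondary outcome is concerned, and the mortality primary outcome is untouched. The priority is low, but the change is cheap and is best made before fall data are examined by arm.

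**What to change.** Under Outcome Measures and Data Sources:

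1. Pre-specify the CDW codes and encounter types that define a fall, and apply them identically in both arms.
2. For the between-arm comparison, exclude falls recorded only at TeleGRACE/GRACE encounters. Apply the same filter in the per-protocol and dose-category comparisons.
3. Report two sensitivity analyses: all recorded falls, and falls leading to an ED visit or admission. State that the second may itself be affected if the program changes acute-care use.
4. Reword the statement on the shared source so that it claims a common source and not equal detection.

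The filter has a limit. The program works with primary care, so a fall found by the team could be passed on and recorded there. Conversely, a program contact could replace a primary care contact at which the fall would have been noted. The two sensitivity analyses help the reader judge both.

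The cost is a few lines in the SAP, a code filter, and somewhat fewer events and less precision for falls. No new data collection is needed.
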